8. ADVERSE EVENT REPORTING

8.1. Adverse Events

8.1.1. Definition

AE is defined as adverse medical events that occur after the subject who receives a drug in clinical trial, but do not necessarily have a causal relationship with the treatment. Refer to Section 8.3 for details on the AE collection period. AE can be any undesirable and unexpected symptom, sign, laboratory abnormality or disease, including at least the following conditions:

- 1) Aggravation of existing (prior to enrollment of clinical trial) medical conditions/disease (including exacerbation of symptoms, signs, laboratory abnormalities);
- 2) Any new occurrence of AE: any adverse medical conditions newly occurred (including symptoms, signs, newly diagnosed diseases);
- 3) Abnormal laboratory test or result of clinical significance.

The investigator should carefully record any AE occurs in the subjects, including: the description of adverse event and all relevant symptoms, time of onset, severity, the correlation-ship with investigational drugs, duration, actions taken against the study drug, final outcomes and prognosis.

8.1.2. The Judgment Standard on Severity of AE

Refer to NCI-CTC AE v4.03 grading criteria for AEs related drugs. Refer to the judgment criteria in Table 9 if any AE is unlisted in NCI-CTCAE v4.03.

Table 9. The Judgment Standard on Severity of AE

| Grade | Clinical Description of Severity |
|-------|--|
| 1 | Mild; without clinical symptoms or mild clinical symptoms; only with clinical or laboratory abnormalities; no treatment is required. |
| 2 | Moderate, requiring minimal, local or non-invasive treatment; age-appropriate limits in Activities of Daily Living (ADL); involving tools refer to cooking, shopping, calling, counting money, etc. |
| 3 | Severe conditions or serious medical symptoms but not life-threatening; leading to hospitalization or hospitalization prolonged; leading to disability; limited in self care ADL. Daily self-care includes bathing, dressing, undressing, eating, going to the bathroom, |

| | |
|---|---|
| | medication, and so on, non-bedridden. |
| 4 | Life-threatening; emergency treatment is required |
| 5 | Leading to death |

8.1.3. Causality Assessment

Collection of AE starts from the signing of informed consent, records are collected regardless of whether the event is related to the investigational drug, whether the subject is assigned to the experimental arm, or even whether the drug is used or not. Any discomfort or abnormal change in objective laboratory tests during the treatment should be recorded accurately. Meanwhile the severity, duration, management and outcome of the AE should be recorded. The investigator should determine the relationship between AE and study drugs, such as whether the occurrence of AE has relationship with a reasonable medication order, the properties of study drug, toxicological and pharmacological effects of study drug, subjects' use of other concomitant drugs, subjects' underlying diseases, medical history, family history and provocative and re-provocative reactions, etc. The causality relationship between AE and study drug will be assessed to be "related" or "unrelated" which are described in the following.

Related: there is a rational relationship between AE and the study drug, the AE can be attributed to the study drug medically (pharmacologically or clinically).

Unrelated: there is lack of rational relationship between AE and the study drug, and the AE can not be attributed to the study drug medically (pharmacologically or clinically), and/or there is other rational reason to explain it, such as underlying disease, complication, and concomitant medications.

8.2. Serious Adverse Events

8.2.1. Definition of SAE

Serious adverse event (SAE) is defined as the medical events that require hospitalization or prolonged hospitalization, disability, limiting working ability, life-threatening or death, and leading to congenital malformation during the clinical trial. Including the following medical events:

- Events leading to death;
- Life-threatening events (defined as the subject has a risk of immediate death);
- Events requiring hospitalization or prolonged hospitalization;
- Events that result in persistent or severe disability / dysfunction / limiting working ability;
- Congenital abnormalities or birth defects;

- Other significant medical events (defined as the event threatens the safety of the subject, or requires intervention measures for the prevention of any of the above conditions).

8.2.2. Hospitalization

Adverse event which causes hospitalization (even less than 24 hours) or prolonged hospitalization should be considered as serious adverse event.

Hospitalization does not include the following:

- Rehabilitation facilities
- Nursing homes
- Routine emergency room admissions (within 24 hours);
- Same day surgeries (as outpatient/same day/ambulatory procedures)
- Social reason (medial insurance reimbursement, etc.)

Hospitalization or prolongation of hospitalization which are unrelated to the exacerbation of adverse events will not be considered as serious adverse events. For example,

- Admission for treatment of a preexisting condition without the development of new adverse events or worsening of the preexisting condition (e.g., for check of persistent pre-trial laboratory test abnormality);
- Administrative admission (e.g., for yearly physical exam);
- Hospitalization as per the trial protocol during the study (e.g., as required by the protocol);
- Elective admission not associated with the aggravation of adverse events (e.g., elective surgery);
- Predefined treatments or surgical procedures should be documented throughout the study program and/or in the baseline data of individual subject;
- A subject is hospitalized due to only use of blood products.

Diagnostic or therapeutic invasive (e.g., operation) and non-invasive procedures should not be reported as AE, but if the disease condition leading to the operation should be reported if it conforms to the definition of AE, eg, acute appendicitis during the AE reporting period should be reported as AE; therefore, the appendectomy should be recorded as the treatment of AE.

8.2.3. Disease Progression and Death

Disease progression is defined as the exacerbation of the subject caused by indications of the study drug, including radiological progression and progression of clinical symptoms and signs. New metastases relative to the primary tumor and the progression of the original metastases are both considered to be progressive disease. Events that are life-threatening, requiring initial or prolonged hospitalization due to symptoms and signs of disease progression, which can lead to permanent or severe disability /

dysfunction / limiting work ability, congenital abnormalities or birth defects are not reported as SAE. If there is any uncertainty about whether SAE is caused by the progression of disease, it should be reported as SAE.

The word “disease progression” should not be reported as an AE or SAE term as disease progression is an expected occurrence in the study population. If any disease progression occurs, the occurrence that confirms disease progression should be reported as an AE. For example, if the subject has epilepsy that is determined to be related with brain metastasis, epilepsy should be recorded as the AE term, rather than disease progression or brain metastasis.

All cases of death that occur during the study period must be reported as SAEs, whether or not the subject has received other antitumor therapy (see Section 8.3). The death resulted from the symptom and sign of progression of disease should be recorded in eCRF and reported as a SAE. The word “death” should not be reported as an AE or SAE term, but as the outcome of the event; the AE that causes or contributes to the fatal outcome should be recorded as the single medical concept. If the cause of death is unknown and cannot be ascertained at the time of reporting, record “unexplained death.”

8.2.4. Reporting Procedures of SAE

In case of SAE, regardless of first report or follow-up report, the investigator must fill in the “serious adverse event report form” immediately, sign and date it, report it to the sponsor within 24h after learning of it, and report it to relevant organizations in time as required by regulations.

The detailed record content of SAE should include symptoms, severity, and association with investigational drugs, time of onset, time of treatment, measures taken, follow-up time and method as well as outcome. If the investigator considers that a serious adverse event is not related to study drug while potentially related to the study conditions (e.g., termination of the original treatment or complications during the trial), the relationship should be described in detail in the narrative section of SAE report form. If there is a change in the severity of an ongoing serious adverse event or its relationship with the study drug, follow-up reports should be submitted immediately. If misinformation is considered to be present in the previously reported SAE, it can be corrected, withdraw or degraded in the follow-up report, and reported in accordance with the SAE reporting procedures.

The sponsor’s email to receive safety reports (SAE, SIE, pregnancy) in this study: [contact]

8.3. Collection and Follow-Up of AE/SAE

The period for AE/SAE collection begins from the time that the subject provides informed consent, through and including 90 days after the last dose of SHR-1210 or 30 days after the last dose of targeted anti-angiogenic therapy, whichever comes later. SAEs that occur after this period, if suspected to be related to study drug, should also be collected. An AE/SAE will be followed up until it is resolved, returns to the baseline level or \leq Grade 1, or reaches a stable state, or until other reasonable time points (e.g., loss of follow-up, death). Every effort should be made to ensure that the subject

achieves the best outcome and definite causality assessment is obtained.

Investigators should inquire about AE/SAE after the last visit at each visit and provide follow-up data in time according to the sponsor's queries.

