| Demographics | X | | X | | X |
| Physical examination ^d | X | X | X | | X |
| Vital signs ^d | X | X | X | | X |
| Body surface area (BSA) ^e | | X | | | X |
| ECOG PS | X | X | X | | X |
| EKG | X ^f | | X | | X |
| AE ^d | X | X | X | X | X |
| Concomitant medication | X | X | X | X | X |
| Quality of life ^l | X | | X | | X |
| Laboratory examination | | | | | |

SCHEDULE OF ACTIVITIES

| Item/evaluation time | Screening period ^a | Treatment period | Follow-up period | |
|--|-------------------------------|----------------------|---|--|
| | | Treatment period | Every 8 weeks in 36 weeks until PD ^b | End-of treatment visit |
| Hematology | X | D1 X ^h | D8 | D15 D22 D29 |
| Liver and kidney function, blood electrolyte | X | X ^h | | X X X |
| Urinary pregnancy test ^l | X | | | |
| Study treatment | | | | |
| Apatinib Mesylate Tablets 500mg | | X ^m | X ^m | X ^m X ^m X ^m |
| SHR-1210 200mg Q2W (for 36 weeks) | | X | | X |
| Curative effect | | | | |
| Tumor imaging evaluation | X ^b | | | X ^b X ^b X ^b |
| AE | X ^k | | | X ^k X ^k X ^k |

BSA = body surface area; ECG = electrocardiogram; PD = disease progression;

- The informed consent should be signed within 2 weeks before the medication. Screening evaluation should be completed within 2 weeks before medication.
- The disease was assessed using the same radioimaging techniques (CT scan or MRI), every 8 weeks during the treatment period and every 12 weeks during the follow-up period until the disease progressed, the subjects began follow-up anti-cancer treatment, the end of the study or the subjects died. Disease assessment should include enhanced CT or MRI of the primary tumor site, chest plain CT, ECT whole body bone imaging or whole body PET/CT examination.

- c. Subjects will continue to receive research medication until the disease progresses or unacceptable toxicity occurs. End-of-treatment visits should be conducted within 4 weeks of the last drug administration and adverse events within 4 weeks of the last drug administration should be recorded.
- d. The abnormal changes of clinically significant physical examination results (including vital signs and ECOG physical condition score) should be recorded as adverse events, and PD should not be reported as adverse events.

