- e. does not need to recalculate BSA every cycle unless the research center guidelines require or subjects to gain or lose more than 10% of their original weight. For obese subjects (BMI > 30), BSA should be calculated using ideal body weight throughout the study period.
- f. To record adverse events within 4 weeks after the last administration of the drug. Drug-related grade 3 or 4 toxicity was monitored until it was reduced to grade 2 or below, or at least 24 weeks after the last drug administration, whichever was earlier. Liver or cardiac toxicity of grade 2 to 4 was monitored until it dropped to grade 1 or below, or at least 24 weeks after the last administration of the drug, whichever was earlier.
- g. Records only the date when new cancer treatments are initiated.
- h. Laboratory results must be obtained within 48 hours before administration.
- i. applies only to women of childbearing age who have sex.
- j. Survival status should be followed up at least every 12 weeks within 2 years after the last administration of the drug, and then every 24 weeks until the end of the clinical study.
- k. The formula of creatinine clearance was: $\text{Cr} = (140 - \text{age}) * \text{body weight}(\text{kg}) / [72 * \text{Scr}(\text{mg/dl})]$ or $\text{Cr} = [(140 - \text{age}) * \text{body weight}(\text{kg})] / [0.818 * \text{Scr}(\text{umol/L})]$. Women were calculated by the result *0.85

ABBREVIATIONS

| Abbreviations | Definition |
|------------------|---|
| AE | adverse event |
| ADA | antidrug antibody |
| ALP | alkaline phosphatase |
| ALT | alanine aminotransferase |
| AST | aspartate aminotransferase |
| AUC | area under the concentration time curve |
| BID | twice daily |
| BOR | best overall response |
| BUN | blood urea nitrogen |
| CK | creatinine kinase |
| C _{max} | maximum concentration |
| Cr | creatinine |
| CT | computed tomography |
| CTLA4 | cytotoxic T lymphocyte antigen 4 |
| D | Day |
| DCR | disease control rate |
| DNA | deoxyribonucleic acid |
| DoR | duration of response |
| eCRF | electronic case report form |
| ECOG-PS | Eastern Cooperative Oncology Group- Performance Status |
| EDC | electronic data capture |
| EORTC | European Organization for the Research and Treatment of Cancer |
| FAS | full analysis set |
| G-CSF | granulocyte colony-stimulating factor |
| GCP | Good Clinical Practice |
| GGT | γ-glutamyl transferase |
| GHS | general health status |
| h | hour |
| HBsAg | Hepatitis B surface antigen |

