6.4. Follow-up Period

Follow up period is initiated when the end-of-treatment visit is completed. 30 days (± 7 days) after the last dose of study drug, subjects must return to the study center for safety follow-up and complete the following parameters for safety evaluation, regardless of initiation of new antitumor therapy. The telephone follow-up will be performed 60 days (± 7 days) and 90 days (± 7 days) after the last dose of study drug, only the survival status, subsequent antitumor therapy, concomitant medication/therapy and AEs/SAEs within the timeframe specified in the protocol need to be collected. If the subject could not resume study drug for AE, the latest date of

administration is used as the date of last dose. If the date has exceeded 30 days (+7 days) over the date when the subject needs to be withdrawn from the study treatment by judgment, the situation does not need to be recorded as deviation from protocol but the subject is recommended to return to the study site as soon as possible for safety visit.

- Hematology: including complete blood count and category (white blood cell, red blood cell, lymphocyte, monocyte, neutrophil, basophil, eosinophil), hemoglobin, platelet count;
- Urinalysis: including white blood cell, red blood cell, urine protein. In case urine protein is $\geq 2+$, 24h urine protein quantification must be added;
- Blood biochemistry: including ALT, AST, total bilirubin, γ -glutamyl transferase (GGT), direct bilirubin, indirect bilirubin, ALP, LDH, albumin, blood urea nitrogen [BUN] or serum urea, creatinine, blood glucose, amylase (lipase test needs to be added if amylase level is abnormal and clinically significant);
- Blood electrolytes: including potassium, sodium, chlorine, calcium, magnesium, phosphorus;
- 12-lead ECG (measured after sitting still for at least 5 minutes): heart rate and QTc interval (calculated using Fridericia's formula);
- ECOG-PS score (see APPENDIX 2 for details);
- Weight and physical examination of important sites: cutaneous system, respiratory system, cardiovascular system, abdomen and mental state. In addition, physical examination of reactive capillary endothelial proliferation needs to be performed on the experimental arm;
- Vital signs (performed after sitting still for 5 minutes): including temperature, blood pressure, pulse rate and respiratory frequency;
- Thyroid function (FT3, FT4, TSH);

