10.4.9. Safety Analyses

10.4.9.1. Analyses of Adverse Events

Adverse events will be coded to MedDRA (v 18.1 or higher) for lower level term (LT), preferred term (PT) and primary system organ class (SOC).

A treatment-emergent adverse event (TEAE) is defined as an adverse event (AE) that had an onset date after the start of the study treatment or that worsened in severity from baseline (pretreatment).

Only those AEs that were treatment-emergent will be included in summary tables. All AEs, treatment-emergent or otherwise, will be presented in subject data listings.

The incidence of TEAEs will be reported as the number (percentage) of subjects with TEAEs by SOC and preferred term. A subject will be counted only once by the highest severity grade per NCI-CTCAE v4.03 within an SOC and preferred term, even if the subject experienced more than 1 TEAE within a specific SOC and preferred term. The number (percentage) of subjects with TEAEs will also be summarized by relationship to the study drug. Treatment-related AEs include those events considered by the investigator to be definitely, possibly related to study treatment or with missing assessment of the causal relationship.

Subject incidence of AE, SAE, AE with CTCAE Grade ≥ 3 , SAE with CTCAE Grade ≥ 3 , drug related AE, drug related SAE, AE with incidence $\geq 5\%$, SAE with incidence $\geq 5\%$, AE leading to dose adjustment, AE leading to discontinued treatment etc. will be tabulated by experimental arm. Time-to-adverse events of special interest, and duration of events will be analyzed using K-M method.

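### Schedule of Activities footnotes c and f give a 4-week post-dose window for recording adverse events, which contradicts the Section 8.3 window of up to 90 days

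*Protocol*

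**What the plan says.** The protocol gives two post-dose periods for recording adverse events.

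- **Section 8.3** starts collection at informed consent and runs it "through and including 90 days after the last dose of SHR-1210 or 30 days after the last dose of targeted anti-angiogenic therapy", whichever is later. It adds: "SAEs that occur after this period, if suspected to be related to study drug, should also be collected".
- **Schedule of Activities, footnote c**, on the end-of-treatment visit, says that "adverse events within 4 weeks of the last drug administration should be recorded".
- **Schedule of Activities, footnote f**, opens with the same period: "To record adverse events within 4 weeks after the last administration of the drug". It then turns to toxicity that is already present: "Drug-related grade 3 or 4 toxicity was monitored until it was reduced to grade 2 or below", with an alternative limit of 24 weeks.
- **Section 6.4** has a safety visit at 30 days (±7) and telephone calls at 60 and 90 days (±7). At the calls, "AEs/SAEs within the timeframe specified in the protocol need to be collected"; no section number is given.
- **Section 8.1.1**, which defines an AE, sends the reader to Section 8.3 for the collection period.
- **Section 10.4.9.1** counts as treatment-emergent an event that "had an onset date after the start of the study treatment or that worsened in severity from baseline". It sets no end date after the last dose.

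Incidence and severity of AEs and SAEs is a secondary endpoint in the Synopsis and in Section 2.

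**The concern.** The schedule is the page that study staff usually work from, and both of its footnotes on this point give a period shorter than Section 8.3. Someone who follows them has no instruction there to record a new event that starts in week 6 after the last infusion, although Section 8.3 requires it. The protocol itself treats SHR-1210 as needing longer surveillance, with 90 days against 30 for the anti-angiogenic drug, and Section 1.3.1 lists immune-related reactions such as pneumonitis, hepatitis and myocarditis as potential risks.

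Because the treatment-emergent definition has no end date, the period actually used for recording decides what enters the safety tables. Later analysis cannot restore an event that was never recorded.

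**Working it through.** The protocol states no figure to reproduce. The check compares the two window ends.

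**Inputs**
- Schedule footnotes c and f: 4 weeks × 7 = 28 days after the last administration of drug.
- Section 8.3: the later of 90 days after the last SHR-1210 dose and 30 days after the last anti-angiogenic (apatinib) dose.
- Sections 5.1.5 and 5.1.6.1.4: either drug may be continued alone after the other is stopped, so the two last-dose dates can differ.

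**Formula.** Let apatinib continue alone for *d* days after the last SHR-1210 dose, and count from the last apatinib dose as day 0.
- Section 8.3 window ends at max(90 − *d*, 30).
- Schedule window ends at 28.
- Shortfall = max(90 − *d*, 30) − 28 = max(62 − *d*, 2).

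If SHR-1210 is the last drug given, both windows count from that dose, and the shortfall is 90 − 28 = 62 days.

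| Case | Section 8.3 ends (days after last drug) | Schedule ends | Shortfall |
|---|---|---|---|
| Both stop together, or SHR-1210 stops last | 90 | 28 | 62 days |
| Apatinib alone for 30 days | max(60, 30) = 60 | 28 | 32 days |
| Apatinib alone for 60 days or more | 30 | 28 | 2 days |

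The maximum is 62/90 = 69% of the post-dose window. The shortfall is never zero, because 28 days is shorter than both limbs of Section 8.3.

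**Does other text close the gap?**
1. *The 24-week monitoring in footnote f.* No. It follows toxicities that already exist and does not capture new onsets.
2. *Section 6.4.* Its contacts fit the 90-day window. Under a 28-day window, the 60- and 90-day calls would have no new-onset AEs in range, and the 30-day visit itself is nominally past the limit. But the section refers to the period only in general terms.
3. *Section 8.1.1.* It points to Section 8.3. That identifies where the period is defined, although no sentence says that Section 8.3 overrides the schedule.
4. *Separate reporting duties.* Section 8.4 requires immune-related AEs of Grade 3 or above to be reported within 24 hours of awareness, with no stated end date. Section 8.3 takes suspected-related SAEs even after its window. Section 8.2.3 treats all deaths in the study period as SAEs.

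Item 4 leaves exposed mainly non-serious Grade 1-2 events, and non-fatal SAEs not judged related, with onset between day 29 and the end of the Section 8.3 window.

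**The case against.** The strongest reply is that the protocol already settles the matter. Section 8.1.1 names Section 8.3, and the 60- and 90-day calls make sense only under its window. A reader might infer from the conflict that nothing indicates which period applies; the documents do not support that. This part of the reply stands, and it is why the footnotes are the text to change.

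A second reply is that neither footnote tells staff to stop at 4 weeks. Footnote c belongs to the end-of-treatment visit, and both can be read as minimum instructions. The footnote letters in the extracted table also do not match their rows reliably, so their exact placement cannot be judged. This is fair, but a footnote that gives a recording period and mentions no longer one will naturally be taken as the period.

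Three stronger readings are tempting and should not be drawn:
- *Late immune-related events as a class would be lost.* The separate duties for Grade 3 or higher immune-related AEs, related SAEs and deaths carry no 28-day limit.
- *The safety results would be uninterpretable.* This is a single-centre, single-arm trial with descriptive safety summaries. There are no sites to diverge and no between-arm comparison to bias, and on-treatment AEs are unaffected. Inconsistency could arise only between staff or patients.
- *69% of events would be missed.* The 69% is a share of post-dose calendar days, and it is the maximum. The documents give no rate of late-onset events.

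**Conclusion.** The contradiction is real and in current text. Footnotes c and f are wrong against Section 8.3, the section that the protocol itself designates. If staff follow the schedule, new AEs after day 28 would be under-counted or inconsistently counted in a secondary endpoint. The gap ranges from 2 to 62 days according to how long apatinib continues after the last SHR-1210 dose.

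This rests on two assumptions: that the footnotes are read as the recording period, and that the event does not fall under one of the separate reporting duties. The documents do not show how many patients will stop both drugs together, so neither the average gap nor the number of events affected can be given. The primary endpoint is not touched. The point is worth correcting because the under-count could not be repaired at analysis.

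**What to change.** Reword the AE-recording period in footnotes c and f to cite the Section 8.3 window. In Section 6.4, replace the general reference to the protocol's timeframe with a reference to Section 8.3 by number, so that the schedule, Section 6.4 and Section 8.3 state one collection period. The remainder of footnote f, on how long existing toxicity is monitored, is a separate rule and is not part of this change.

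The cost is two footnotes and one cross-reference. The 60- and 90-day contacts are already planned, so no visit or call is added. The change concerns data collection only and alters nothing in treatment.
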